Research Protocol

TITLE: the Change of R-spondin Proteins Plasma Concentration Level caused by Mechanical Ventilation and its Effect on Mechanical Ventilation Induced Lung Injury

PROTOCOL ID: XH-17-015

NCT number: NCT03315702

SPONSOR: Xinhua Hospital, Shanghai Jiao Tong University School of Medicine

INVESTIGATOR: [name]

Date : July 20, 2017

Materials and methods

1. Patients recruitment

Research protocol was approved by Xinhua Hospital Ethics Committee Affiliated to Shanghai Jiao Tong University School of Medicine. With written informed consents given by patients undergoing elective surgery, individual information and blood samples were collected.

Inclusion Criteria is shown as followed: patients undergo elective surgery with mechanical ventilation lasting for > 4 hours; classified as physical status I to III according to the American Society of Anesthesiologists Physical Status Classification System; Written informed consent is approved.

Participating subjects with any one of criteria shown as followed were excluded: chronic lung disease; recent lung infection; recent anaesthetics or mechanical ventilation treatment; hemodilution with massive fluid supply during surgery; children; women during pregnancy or lactation; being involved in other clinical subjects.

2. Mechanical ventilation

Mechanical ventilation protocol: tidal volume 6-8 ml/kg, positive end-expiratory pressure 5 cmH₂O, oxygen concentration 40%; respiratory rate 10-15/min, inspiratory/expiration ratio 1:1.5.

3. Blood samples collection and detection

With written informed consents given by patients undergoing elective surgery, collect 2ml venous blood samples each time before endotracheal intubation and third hour after, thus mechanical ventilation for one patient lasts for four hours. Store samples in EDTA plus blood collection tubes. All samples were stored in 4 °C refrigerator and centrifugated in 1hours after being collected. Plasmas were separated from venous blood samples via centrifugation at 4 °C1000rpm for 10 min, and stored in -80 °C before being analyzed with Elisa.

4. Statistical analysis

Analyze R-spondin proteins plasma centration levels of two samples from the same patient collected relatively before endotracheal intubation and fourth hour after as paired-samples. Quantitative data were expressed as mean and 95 % confidence interval (CI) for mean. Differences between paired-samples are assessed by paired *t*-test, performed using the SPSS13.0 package. $P < 0.05$ is considered as statistically significant criteria.

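### The eligibility criteria do not rule out operations that injure the lung directly or interrupt two-lung ventilation, and any such patients enter the same paired t-test

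*Combined protocol and SAP*

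**What the plan says.** All references are to the combined protocol and SAP.

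- **Section 1, inclusion.** The only condition on the operation is "patients undergo elective surgery with mechanical ventilation lasting for > 4 hours". The other conditions are consent and patients "classified as physical status I to III according to the American Society of Anesthesiologists Physical Status Classification System".
- **Section 1, exclusions.** Three items concern the lung's history or previous exposure: "chronic lung disease; recent lung infection; recent anaesthetics or mechanical ventilation treatment". One concerns an event in theatre: "hemodilution with massive fluid supply during surgery", with no threshold. The rest are "children; women during pregnancy or lactation; being involved in other clinical subjects". No item refers to the type of operation.
- **Section 2.** One regimen is given for everyone, beginning "tidal volume 6-8 ml/kg, positive end-expiratory pressure 5 cmH₂O, oxygen concentration 40" (the last figure in per cent), followed by a rate and an inspiratory-to-expiratory ratio. One-lung and interrupted ventilation are not mentioned, and adherence to the regimen is not made a condition of eligibility or analysis.
- **Section 4.** "Differences between paired-samples are assessed by paired *t*-test". There is no stratum, covariate or subgroup by operation, and no comparison group.
- **Title.** The change in R-spondin is described as one that ventilation causes.

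No sample size, SD, expected effect or case mix is stated.

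**The concern.** The exclusions show that the sponsor wanted to remove other explanations for a change: previous lung insults, and dilution of the plasma during surgery. They leave open a more direct competing explanation, namely an operation that itself handles, collapses or resects the lung, or that suspends its ventilation between the two blood samples. Requiring more than 4 hours of ventilation favours longer operations, among which such cases are plausible.

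Two things could go wrong. A patient whose lung is operated on, or collapsed and re-expanded, may show a change that comes from the operation and is read as an effect of ventilation. A bypass patient may have had less ventilation than the interval between samples implies, which would weaken a real effect. In either case the pooled mean would describe an exposure other than the one in Section 2. Unlike the general confounding with surgery and anaesthesia, this part can be removed within the single-group design.

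**Working it through.** **Step 1. Does any rule remove these patients?** The plan gives no figure to reproduce, so the first check sets the rules against the three kinds of operation.

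| Rule | Lung resection | Planned one-lung ventilation | Cardiopulmonary bypass |
|---|---|---|---|
| Elective, ventilated > 4 h | Removes shorter cases only | Removes shorter cases only | Removes some; unclear whether time on bypass counts as ventilation |
| ASA I to III | Removes sicker patients only | Removes sicker patients only | Removes sicker patients only |
| Chronic lung disease, recent infection | Removes some | Removes some | Removes few |
| Hemodilution with massive fluid | Not aimed at these | Not aimed at these | May remove some; no threshold, bypass not named |
| Section 2 regimen | Not an eligibility rule | Not an eligibility rule | Not an eligibility rule |

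The entries are readings of the criteria; the documents give no counts. No column is closed. An ASA II patient with no chronic lung disease or recent infection, having a long elective operation with one lung collapsed, meets every criterion as written.

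**Step 2. What could that do to the test?** Every input here is assumed. Let ventilation alone cause no change, let a share p of patients have such an operation, and let their mean paired difference be shifted by d SDs. The remaining patients have mean 0 and SD 1.

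- Pooled mean shift = p × d.
- Pooled SD = √(1 + p(1 − p)d²).
- Noncentrality of the paired t statistic ≈ p × d × √n / pooled SD.

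For p = 0.2, d = 1, n = 30: shift = 0.2 × 1 = 0.2; SD = √(1 + 0.2 × 0.8 × 1) = √1.16 = 1.077; noncentrality = 0.2 × 5.477 / 1.077 = 1.017. The noncentral t distribution then gives a two-sided rejection probability of about 0.166. Simulation (20,000 replicates) gives 0.163.

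Simulated chance of P < 0.05, two-sided, when ventilation does nothing:

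| p | d | Shift p × d | n = 30 | n = 50 | n = 100 |
|---|---|---|---|---|---|
| 0 | – | 0 | 5% (nominal) | 5% (nominal) | 5% (nominal) |
| 10% | 0.5 | 0.05 | 6% | not run | not run |
| 20% | 0.5 | 0.10 | 8% | 10% | 16% |
| 20% | 1.0 | 0.20 | 16% | 24% | 45% |

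Repeat simulations agreed to within about one percentage point. The excess grows with n because it is bias: a larger sample measures the wrong mean more precisely.

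**Step 3. The opposite direction.** Suppose ventilation does change R-spondin by Δ, and the affected patients show no change because their lungs were largely unventilated. The pooled mean is then (1 − p)Δ, which is 0.8Δ at p = 20%. The same gap can therefore create an apparent effect or dilute a real one, and nothing in the documents says which.

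**The case against.** The case on the other side has four parts.

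1. **The documents show no such patient.** A reader might infer from the open criteria that lung trauma or interrupted ventilation is in fact pooled into the result, or that every kind of elective operation is admitted. Neither follows. No thoracic, one-lung or bypass case is mentioned, and the existing rules remove some candidates. This stands: the defect is that the criteria do not rule these operations out.

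2. **Section 2 may imply that they are not intended.** It describes one regimen, and Section 3 describes ventilation lasting four hours per patient. A bypass or one-lung patient may not fit that description, so the protocol may simply not contemplate them. This narrows the gap without closing it, because neither section is written as a condition for entering the study or the analysis.

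3. **The magnitude is assumed throughout.** n, SD, p and d are all supplied here, and the documents do not show that lung surgery or bypass moves plasma R-spondin. Assuming shifts of 1 to 2 SD in place of 0.5 to 1 takes the rejection probability from 7% (n = 20, 10% affected, 1 SD) to 88% (n = 100, 20% affected, 2 SD). This stands: the figures show a mechanism and do not estimate a bias for this study.

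4. **The larger attribution problem is untouched.** Every patient has surgery and anaesthesia between the samples, with no unventilated comparator, so the 5% baseline in the illustration is itself optimistic. This stands, and it limits what the fix can claim. It is no reason to keep a part of the problem that can be removed cheaply.

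Broad eligibility is also a legitimate choice for an exploratory biomarker study. It would then need operation type recorded and an analysis that uses it; Section 4 has no such analysis.

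**Conclusion.** The point holds as a gap in eligibility. Followed as written, the plan can attribute to mechanical ventilation a change measured in patients who did not receive the continuous exposure of Section 2, or whose lungs were injured by the operation itself. The conclusion rests on the text alone: the single condition on the operation, an exclusion list silent on its type, and one unstratified test.

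The consequence cannot be sized from the documents. On the stated assumptions it runs from negligible (about 6% against 5%) to material (about 16% at n = 30, more at larger n), and dilution of a true effect is equally possible. A reader might go further and infer that the result is invalid, or that closing the gap would let the change be credited to ventilation. The documents support neither: enrolment of such patients is not shown, and surgery and anaesthesia remain confounded with ventilation in everyone else. The change is worth making because it is cheap and concerns the organ under study.

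**What to change.** **Before or during recruitment.** Add to the Section 1 exclusions: operations on the lung or with planned one-lung ventilation; use of cardiopulmonary bypass; any planned interruption of two-lung ventilation between the two blood samples. This can usually be decided from the operating list before the first draw, and it alters no patient's care.

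**If enrolment has started.** Record operation type and any one-lung ventilation or bypass for every patient. State in Section 4, before any assay result is seen, that the paired analysis is made in patients without these features, and report the all-patient result beside it. The timing matters: choosing the analysis set after the concentrations are known would introduce a selection problem of its own.

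**Cost.** One line of eligibility text or one paragraph of analysis text, a smaller recruitment pool, and no conclusion for thoracic or cardiac surgery.

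**Limit.** This removes only one part of the confounding. Without a comparator, the report should describe the result as a change during surgery under anaesthesia and ventilation.

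### The single 1000 rpm spin may leave many platelets in the frozen plasma; a stated higher force would be a cheap safeguard for the only endpoint

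*Combined protocol and SAP*

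**What the plan says.** Section 3 of the combined protocol and SAP sets out the whole sample pathway. On the draws: "collect 2ml venous blood samples each time before endotracheal intubation and third hour after". On the tubes: "Store samples in EDTA plus blood collection tubes". On the delay before the spin: "All samples were stored in 4 °C refrigerator and centrifugated in 1hours after being collected". On the separation: "Plasmas were separated from venous blood samples via centrifugation at 4 °C1000rpm for 10 min", "and stored in -80 °C before being analyzed with Elisa". Only one spin is described. There is no relative centrifugal force, rotor or radius, and no second spin, filtration, platelet count or criterion for platelet-poor plasma.

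Section 4 (Statistical analysis) names plasma R-spondin as the only outcome and compares the two samples directly: "Differences between paired-samples are assessed by paired" *t*-test, with no adjustment for cell counts or dilution. The one safeguard on blood composition is an exclusion in Section 1 (Patients recruitment): "hemodilution with massive fluid supply during surgery".

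**The concern.** A rotor speed does not fix a force. At 1000 rpm an ordinary bench rotor gives a soft spin, which should bring down red cells but may leave platelets suspended. If platelets contain assayable R-spondin, and freezing and thawing releases it, the ELISA would read true plasma protein plus platelet content.

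Pairing removes a platelet contribution that is the same at both draws. It does not remove one that changes between them. The first sample precedes intubation and the second comes hours into surgery, so platelet number or activation could differ. Each sample must be spun within an hour of collection, so the two samples of a pair also go through separate spins. At stake is whether a paired difference in measured concentration can be read as a change in plasma R-spondin. The design has no unventilated group that could reveal a preparation artefact.

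**Working it through.** The plan states no force, so there is no figure of its own to reproduce. The check has four steps.

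**Inputs from Section 3:** 1000 rpm, 10 min (600 s), 4 °C, 2 ml per draw.

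**Assumed inputs (not in the documents):** rotor radius 8-20 cm; swing-out geometry; platelet radius 1.2 µm; density excess over plasma 30-40 kg/m³; plasma viscosity 2.0-2.5 mPa·s at 4 °C; tube bore 9-11 mm; plasma 55-60% of blood volume.

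**1. Force.** RCF = 1.118 × 10⁻⁵ × r(cm) × rpm². At 1000 rpm this is 11.18 × r:
- 8 cm: 89 x g
- 10 cm: 112 x g
- 16 cm: 179 x g
- 20 cm: 224 x g

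Radii of 5 and 25 cm give 56 and 280 x g. Reaching 1000 x g at this speed would need a radius of 1000 / 11.18 = 89 cm.

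**2. Settling distance.** Stokes: distance = 2a² × Δρ × 9.81 × RCF × t / (9η), where a is the platelet radius.
- 89 x g, 600 s: 2.0 mm (Δρ 30, η 2.5) to 3.4 mm (Δρ 40, η 2.0)
- 224 x g, 600 s: 5.1 to 8.4 mm

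The overall range is about 2-8 mm. Red cells (assumed 5.5 µm diameter, density excess 70 kg/m³, viscosity 2.0 mPa·s, crowding ignored) would travel about 31-78 mm at 90-224 x g, so the spin does separate red cells.

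**3. Share left in the plasma.** The relevant height is the plasma layer, not the whole blood column.
- Blood column = 2000 mm³ / (π × bore² / 4): 31.4 mm at 9 mm bore, 21.0 mm at 11 mm
- Plasma layer: from 0.55 × 21.0 = 11.6 mm to 0.60 × 31.4 = 18.9 mm, about 12-19 mm
- Share suspended = 1 − distance / layer: lowest 1 − 8.4/11.6 = 28%; highest 1 − 2.0/18.9 = 89%

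That is roughly 30-90%. A wider set of constants (diameter 2.0-3.0 µm, density excess 20-40 kg/m³, viscosity 1.8-2.4 mPa·s) gives 1.0-5.9 mm at 90 x g and 2.4-14.6 mm at 224 x g. Only its favourable extreme (14.6 mm) clears the shortest layer. Its middle value at 224 x g (5.8 mm) leaves 1 − 5.8/11.6 = 50%.

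For comparison, 2000 x g for 15 min gives 68-113 mm with the first set of constants, which clears every layer considered.

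**4. Effect on the paired difference.** Let f be the platelet share of the first-draw signal and d the relative change in the platelet contribution beyond dilution. The spurious relative change is f × d. The documents give neither term. As what-ifs only: f = 10% and d = −20% gives −2%; f = 20% and d = −30% gives −6%; f = 0 gives 0.

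**The case against.** The strongest objection is that the key link is missing. Nothing in the documents says that platelets hold R-spondin or that this ELISA would detect it. A reader might infer from the soft spin that the endpoint is biased. The documents do not support that; they support only a possible bias. This objection stands, and it limits the point.

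Four further objections have force.

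- **Dilution.** Simple dilution lowers plasma protein and suspended platelets by the same factor, so a dilution correction would rescale both. Only a platelet change beyond dilution belongs to this point. The Section 1 exclusion covers massive fluid supply, not platelets.
- **Noise versus bias.** Differences between spins are random error unless they differ systematically between first and second draws. A larger sample does reduce that part; it does not reduce a systematic shift.
- **Range of force.** The 2.5-fold range, 89-224 x g, reflects an unstated rotor. A reader might take it as variation within the study, but nothing shows that the two samples of a pair were spun differently.
- **A slip for 1000 x g.** If that force was meant, the main constants give about 23-38 mm in 10 min, which clears the plasma layer, and most of the concern falls away. The text as written says rpm, so it would still need correcting.

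None of this rescues the written instruction. At 25 cm radius and the most favourable main constants the distance is 8.4 × 280/224 = 10.5 mm, still short of the shortest layer (11.6 mm).

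**Conclusion.** The point holds as a cheap improvement of lower priority. Followed as written, Section 3 probably leaves a material share of platelets, roughly 30-90%, in the plasma that is frozen and assayed. That range rests on the assumed rotor radius, tube bore, plasma fraction and platelet constants, and on simple settling in a swing-out rotor.

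The consequence for the result is conditional. If platelets carry R-spondin that the ELISA detects, a change in their number or activation between draws, beyond dilution, would bias the paired difference, and non-systematic carry-over differences would add noise. If the platelet share is zero, there is no shift. A reader might take the products f × d as an estimate of the bias. They are not: both terms are assumed, and the plan states no expected change or standard deviation against which to judge them.

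**What to change.** In Section 3, replace the speed and time with a force in x g and a time that yield platelet-poor plasma, consistent with the ELISA kit's sample instructions (not included in the documents). One example is to transfer the supernatant after the first spin and spin it again at about 2000 x g for 15 min at 4 °C before freezing. Require the same centrifuge and settings for both samples of a patient. If rpm was written for x g, or a second spin was done but not described, correct the text accordingly.

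For any pairs already frozen after the 1000 rpm spin:
- keep both samples of a pair on the same preparation;
- flag those pairs;
- if both preparations exist in the study, report the paired test with and without them;
- if all pairs were prepared this way, state it as a limitation.

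The cost is a short edit to the laboratory procedure, about 15-20 minutes of bench time per sample and slightly less plasma per tube. No extra blood or patients are needed.

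### Does leaving the R-spondin proteins unnamed and uncounted leave the plan's only test undefined?

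*Combined protocol and SAP*

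**What the plan says.** The title speaks of "the Change of R-spondin Proteins Plasma Concentration Level", in the plural and without naming a member of the family. Section 3 (Blood samples collection and detection) describes tubes, centrifugation and storage, and says of the assay only that plasma is frozen "before being analyzed with Elisa". Section 4 (Statistical analysis) gives the instruction "Analyze R-spondin proteins plasma centration levels of two samples from the same patient". It then fixes the method, "Differences between paired-samples are assessed by paired" t-test, with P < 0.05 as the criterion, and the summary: "Quantitative data were expressed as mean and 95 % confidence interval (CI) for mean".

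No section lists the proteins, gives their number, makes one of them primary, or mentions a sum, score or other combination. There is no multiplicity rule, and no claim that an error rate is controlled across proteins.

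**The concern.** A paired t-test needs one number per patient per sample. With a plural, unnamed analyte, two analysts could in principle follow Section 4 and test different variables: each protein separately, or one combined level. These are different hypotheses and can give different answers from the same blood samples.

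Two consequences would matter. If several proteins were tested and any one P < 0.05 were reported as a change in R-spondin generally, the chance of a false statement would exceed 5%. And with no list of proteins in the plan, a reader of this document alone could not check that every protein assayed was reported.

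**Working it through.** **1. What is fixed and what is open.** The title and Sections 3 and 4, read together, fix the protein family, plasma as the matrix, ELISA as the method, two samples per patient with the first before intubation, the paired t-test, the summary statistics and the 0.05 criterion. They leave open which proteins, how many, and whether they are tested separately or together. The plan states no sample size, SD, correlation or power, so there is no figure of its own to reproduce.

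**2. The per-protein reading.** Nothing in Section 4 points to combining proteins, so the natural reading is one paired t-test for each. Each test has its own null hypothesis and a 5% error rate for the statement about that protein. This holds for one protein or for several.

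**3. The family reading.** Suppose k proteins (k is assumed) are each tested at 0.05 and any one significant result is taken as a change in R-spondin. With independent tests, the chance of at least one false positive is 1 − 0.95^k:

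| k | 1 − 0.95^k | Upper bound 0.05 × k |
|---|---|---|
| 1 | 5.0% | 5% |
| 2 | 9.8% | 10% |
| 3 | 14.3% | 15% |
| 4 | 18.5% | 20% |

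Positive correlation between the proteins lowers this. At an assumed correlation of 0.95, the range for k = 2 to 4 is 6.5% to 8.0%. The choice between requiring any protein and requiring all of them also matters under this reading. With 80% power each and independence, the two rules disagree with probability (1 − 0.2^k) − 0.8^k. For k = 2 that is 0.96 − 0.64 = 0.32, and for k = 4 it is 0.998 − 0.410 = 0.59 after rounding. Section 4 contains neither rule.

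**4. The combined reading.** Suppose protein A changes, with 80% power on its own (mean z = 2.80, two-sided cut-off 1.96), and protein B does not change. Let q be the SD of B's change divided by that of A's, and r the correlation of the two changes. The test on A + B has mean z = 2.80 / √(1 + q² + 2rq). All of these inputs are assumed, including two-sidedness, which Section 4 does not state.

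- q = 0.1, r = 0: 2.80 / √1.01 = 2.79, power 80%.
- q = 1, r = 0: 2.80 / √2 = 1.98, power 51%.
- q = 10, r = 0: 2.80 / √101 = 0.28, power 6%.
- q = 1/3, r = −0.5: 2.80 / √(1 + 0.111 − 0.333) = 3.17, power 89%.

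If both proteins change in the same direction with 80% power each, mean z becomes 2.80(1 + q) / √(1 + q² + 2rq). Power then runs from 80% to 98% for q from 0.1 to 10 and r from 0 to 0.95.

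**5. What this shows.** A summed outcome could do much better or much worse than separate tests, depending entirely on assumed inputs. Since the plan proposes no sum, the spread does not measure harm in this plan. The figures in step 3 likewise describe decision rules the plan does not contain.

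**The case for a change.** The strongest case for a change is that, when a plan has only one test, naming the variable it is applied to is the least one can ask. It would cost a sentence or two and no extra assays. Separate testing may be the obvious reading, but it does not say which proteins. Stored plasma could be assayed for several, and a reader could not tell from this document whether an unreported one had been dropped.

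The last part stands: a reader cannot audit completeness of reporting from this document alone. That limits transparency, but it does not make any reported paired t-test wrong. The documents give no sign that proteins would be selected by result, and a list would not alter the test, its level or the data collected. Nor has a specific error been shown in the planned summaries that would require a mean paired difference with its interval to be added.

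A separate inconsistency touches the same sentence of Section 4. Section 3 takes the second sample "before endotracheal intubation and third hour after", while Section 4 pairs samples taken "before endotracheal intubation and fourth hour after as paired-samples". Those two statements must be reconciled, but that is a different point, and naming the proteins would not settle it.

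**Conclusion.** No change to the plan is needed on this point. The proteins are indeed neither named nor counted, but to call the outcome undefined goes too far. Followed as written, Section 4 gives one valid 5% paired comparison for each protein measured. What is missing is a list that has to exist before the assay can be run, so this is a gap that the laboratory and analysts fill sensibly in ordinary work.

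On the per-protein reading the effect on error rates is nil. The 9.8% to 18.5% range applies only if two to four independent proteins are tested and any one significant result is stated as a finding about R-spondin as a whole. The 6% to 98% power range applies only to a summed outcome. The plan adopts neither. This conclusion rests on reading Section 4 as separate tests and on each result being stated as a result about that protein. If a report claimed a general R-spondin change from one of several proteins, that claim would be open to criticism in the report itself.

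### Does Section 4 leave the within-patient change without an interval, and should the paired t-test be moved to the log scale?

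*Combined protocol and SAP*

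**What the plan says.** Section 4 is the whole of the statistical plan. It treats the "two samples from the same patient collected relatively before endotracheal intubation and fourth hour after as paired-samples". It then says "Quantitative data were expressed as mean and 95 % confidence interval (CI) for mean", and the next sentence reads "Differences between paired-samples are assessed by paired" t-test, with significance at P below 0.05. Section 3 adds only that plasma is "stored in -80 °C before being analyzed with Elisa".

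Section 4 does not say whether the mean and interval apply to each time point, to the paired differences, or to both. It mentions no transformation, distribution check or alternative test. The documents give no sample size, SD, coefficient of variation (CV), within-patient correlation, expected change or assay limit.

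Sections 3 and 4 also give different hours for the second sample. That is a separate matter and does not bear on this point.

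**The concern.** The protocol title makes the change in plasma concentration the object of study. Read in order, Section 4 appears to give an interval to the concentrations and only a P value to the change. Intervals for two time-point means carry the full spread between patients, which pairing removes, so they are the wrong error bars for a paired comparison. With no sample size stated, a non-significant P value reported alone could not be told apart from an imprecise study.

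The second worry is scale. Concentrations are positive. If they are right-skewed and ventilation multiplies them, a few patients with high values dominate the raw difference and the raw t-test loses power. A paired analysis of log concentrations, reported as a geometric mean ratio with its interval, would appear to cure both problems for a sentence or two of text.

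**Working it through.** **Inputs.** From Section 4: one group, two samples per patient, paired t-test, 0.05 level. Sidedness is not stated; two-sided is assumed. Everything else is assumed for illustration. There is no stated figure to reproduce.

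**1. Is the interval for the change really missing?** With mean difference d, SD of differences s and n pairs, the planned test is t = d / (s/√n). The 95% interval is d ± t(0.975, n−1) × s/√n. It uses the same three quantities, and it excludes zero exactly when two-sided P is below 0.05. Stating it in the plan changes neither the test nor the conclusion.

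With complete pairs, d is also the difference of the two reported means. An exact P value and n give |t|, and then s/√n = |d|/|t|. Two means, n and an exact P value are therefore enough to recover the interval.

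**2. How misleading would time-point intervals be?** With equal SDs and correlation r, the SD of the difference is SD × √(2(1−r)).

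- Interval for the change relative to a time-point interval, √(2(1−r)): 1.18, 1.00, 0.63 and 0.45 at r = 0.3, 0.5, 0.8 and 0.9.
- Interval built as if the two samples were independent, relative to the paired one, 1/√(1−r): 1.41, 1.83 and 2.24 at r = 0.5, 0.7 and 0.8.
- Difference at which the two intervals stop overlapping, relative to the paired significance threshold, 2/√(2(1−r)): 2.0, 2.6 and 3.2 at the same r.

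The arithmetic is right, but Section 4 neither builds an interval this way nor judges by overlap. It uses the paired test. These factors measure a reader's mistake and not a planned analysis.

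**3. Would the log scale be better?** Each setting used 20,000 simulated trials and two-sided 5% paired t-tests on raw differences and on log-ratios, with n = 40. In the lognormal settings the log SD is √ln(1+CV²) and r is the log-scale correlation.

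| Assumed truth | Raw power | Log power | Log minus raw |
|---|---|---|---|
| Lognormal, ratio 1.25, r 0.5, CV 30% | 99.5% | 99.7% | +0.2 |
| Same, CV 50% | 76.5% | 82.8% | +6.3 |
| Same, CV 100% | 26.5% | 37.7% | +11.2 |
| Same, CV 100%, r 0.8 | 52.2% | 74.1% | +21.9 |
| Normal levels, CV 30%, r 0.5, shift of 15% of the mean | 87.0% | 83.5% | −3.5 |
| Lognormal baseline, CV 100%, median 1, additive change 0.1, noise SD 0.2 | 88.1% | 40.1% | −48.0 |

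In the last setting very low second values were floored at 0.02. A second run of that setting put log power at 43%, with raw power again 88%.

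The same contrast appears at n = 30. With a ratio of 1.3, CV 100% and r 0.8, power was 54% raw against 75% log. With an additive change of 0.1 on a lognormal baseline of CV 50% (noise SD 0.2), it was 76% raw against 49% log.

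The last table row shows why skewed levels alone do not decide the matter: the paired t-test depends on the distribution of the differences.

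**4. Is the planned test valid?** With no change, in lognormal settings with n from 20 to 60, CV from 30% to 150% and r of 0.5 or 0.8, the raw test rejected in 3.3% to 5.1% of trials and the log test in 4.7% to 5.4%. The raw test is somewhat conservative when skew is strong. It does not inflate false positives.

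**The case for a change.** The strongest case for a change is that the plan does not commit to reporting the effect with its precision. An ambiguous sentence binds nobody, and a report could give two time-point intervals and the word significant. With no sample size rationale, an interval is the reader's only guide to what a null result means, and asking for it costs one sentence. It is also true that, if R-spondin is strongly skewed and changes multiplicatively, the log analysis is clearly more powerful and its ratio describes the typical patient better.

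The first part stands as a remark on reporting. Section 4 does not name the interval for the change, and a good report will give it. But the sentence on means and intervals can cover the paired differences as well as the concentrations, so it is an inference that it covers only time points. Nothing in Section 4 prevents the interval from being reported, and calculating it leaves the analyst no choices that could bias the result.

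The second part stands only on its condition. The documents do not say that the levels are skewed or that the change is multiplicative. Making the log-ratio primary would also replace the mean difference with a ratio of geometric means, and would require a rule for values below the assay limit. A log-scale sensitivity analysis is reasonable and needs no amendment.

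**Conclusion.** No change to the plan is needed. The missing mention of an interval for the change is a reporting gap with one obvious filling: the mean paired difference and its standard error are already part of the planned test, and the P value and conclusion stay the same. The raw scale is a fair choice given what is known. In the n = 40 scenarios tabulated, the log test's advantage ran from about 22 points of power to a loss of about 48, depending on whether the change is multiplicative or additive. Type I error of the planned test was at most about 5% in every null setting run.

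These figures rest on assumed sample sizes, CVs, correlations and effects, since the documents supply none. They show that the direction of any gain is open; they do not estimate the power of this study. Evidence that the within-patient change is proportional to baseline would favour the log scale. Without it, there is no basis for overriding the planned test.
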